ASES	American Shoulder and Elbow Surgeons
CI	Confidence Interval
CIP	Clinical Investigation Plan
CRF	Case Report Form
eCRF	Electronic Case Report Form
EDC	Electronic Data Capture
HA	Hemi-Shoulder Arthroplasty
ICF	Informed Consent Form
IFU	Instructions for Use
IRB	Institutional Review Board
ITT	Intent-to-Treat
LTFU	Lost to Follow-Up
PP	Per Protocol
RSA	Reverse Shoulder Arthroplasty
SADE	Serious Adverse Device Effect
SAE	Serious Adverse Event
SAP	Statistical Analysis Plan
TSA	Total Shoulder Arthroplasty
UADE	Unanticipated Adverse Device Effect

2. Synopsis

Title	A Post-Market Clinical Evaluation of the ReUnion Total Shoulder Arthroplasty (TSA) System
Treatment	ReUnion TSA System
Design	
• Post-Market• Multicenter• Prospective• Non-Randomized
Objectives	
The objective of this clinical investigation is to demonstrate the safety and efficacy/performance of the ReUnion TSA System.
 
Efficacy/performance of the procedure will be measured the American Shoulder and Elbow Surgeons (ASES) Shoulder Score.
 
Safety of the ReUnion TSA System will be demonstrated through reporting of device-related intra-operative and post-operative Adverse Events (AEs).

Target Population	100 subjects are to be enrolled in this clinical investigation. Enrolled subjects will be assessed at Pre-Operative, Operative/Discharge, and at 6 Weeks, 6 Months, 12

	Months, 24 Months and annually thereafter up to 10 years following the index procedure.
Endpoints	
Primary Endpoint:
 
The objective of the clinical investigation is to demonstrate the efficacy/performance of the device at 24 months, as measured by the ASES Shoulder Score.
 
Secondary Endpoints:
 
 • Safety: Incidence of device-related intra-operative and post-operative AEs • Efficacy/Performance: Implant survivorship will be monitored
Inclusion Criteria:	
 a. Subject is willing to sign the informed consent. b. Subject is willing and able to comply with post-operative scheduled clinical assessments. c. Subject is male or non-pregnant female and 18 years or older at the time of surgery. d. Subject has one or more of the following: 
 • Aseptic necrosis of the humeral head • Painful, disabling joint disease of the shoulder resulting from degenerative arthritis, rheumatoid arthritis or post-traumatic arthritis • Failed previous total shoulder replacement, resurfacing or other procedure
Exclusion Criteria:	
 a. Subject has an active or suspected latent infection in or about the shoulder joint. b. Subject has mental or neuromuscular disorder which would create an unacceptable risk of prosthesis instability, prosthesis fixation failure or complications in postoperative care. c. Subject has bone stock compromised by disease, infection or prior implantation which cannot provide adequate support and/or fixation to the prosthesis. d. Subject has anticipated activities which would impose high stresses on the prosthesis and its fixation. e. Subject is obese such that he/she produces a load on the prosthesis which can lead to failure of fixation of the device or to failure of the device itself. f. Subject has absent, irreparable or non-functioning rotator cuff and other essential muscles. g. Subject has concomitant disease(s) which may significantly affect the clinical outcome. h. Subject has traumatic or pathologic fracture of the proximal humerus.

3. General Information and Administrative Structure

3.3. EDC SYSTEM

Name: IBM Clinical Development
Email: [contact]
[contact]

4. Product Information

All components of the ReUnion TSA System have been cleared and approved for sale and use in the United States prior to starting the clinical investigation. 510(k) Clearance was received on 05May2011. This system is to be used only for indications for which it has been approved. Please see the approved Instructions for Use (IFU) and Operative Technique manuals for a detailed description of the medical device(s) and instrumentation as well as the intended use information.

Medical device product traceability will be achieved by capturing the implant lot number.

5. Risks and Benefits

This prospective, multicenter clinical investigation is designed to examine the safety and performance of the ReUnion TSA System in accordance with the approved IFU, labelling and instrumentation. The potential risks to subjects are described in the approved IFU and Operative Technique manuals.

Potential benefits resulting for the ReUnion TSA System over other devices and procedures as demonstrated by superior scoring on the outcome survey and positive results on other clinical evaluation measurements would suggest affirmative clinical efficacy.

6. Introduction

The ReUnion TSA System is designed as an anatomical total shoulder or hemi-shoulder endoprosthesis to address advanced arthritic disorders affecting the shoulder joint in subjects having intact or repairable rotator cuff function. The ReUnion TSA System consists of a completely modular shoulder platform including a Humeral Stem, Humeral Head and Glenoid. The intended purposes of the ReUnion TSA System are to achieve pain relief, improvement of range of motion and restoration or improvement of the shoulder function while ensuring long-term replacement of the shoulder joint with sufficient stability of all endoprosthesis components.

7. Clinical Investigation Design

This investigation is a prospective, multicenter clinical investigation. It is anticipated that a total of one hundred (100) subjects will be enrolled at approximately 4-7 sites. Neither subjects nor investigators are blinded to treatment and the clinical investigation does not include a contemporaneous control. The clinical investigation has been designed to follow the surgeon's standard of care for joint arthroplasty subjects, which entails clinical evaluation on a regular ongoing basis, or as needed should the subject become symptomatic in the treated joint. The enrollment period is expected to occur over 14 months.

8. Objective

8.1. PRIMARY ENDPOINT

The primary endpoint of the clinical investigation is to demonstrate non-inferiority of the device to the selected literature controls, as measured by the ASES Shoulder Score at 24 Months post-operative.

8.2. SECONDARY ENDPOINT

In addition to the principal endpoint, information on the following outcomes will be assessed up to 10 years after the index procedure:

Safety: Incidence of device-related intra-operative and post-operative AEs

Efficacy: Implant survivorship

9. Selection of Clinical Investigation Population

Subjects participating in this clinical investigation will be recruited from the investigator's standard subject population, where all subjects presenting for primary or revision total shoulder replacement will be evaluated for clinical investigation participation based on the eligibility criteria listed below.

9.1. INCLUSION CRITERIA

- a. Subject is willing to sign the informed consent.
- b. Subject is willing and able to comply with postoperative scheduled clinical and radiographic evaluations.
- c. Subject is male or non-pregnant female and 18 years or older at the time of surgery.
- d. Subject has one or more of the following:
 - Aseptic necrosis of the humeral head

- Painful, disabling joint disease of the shoulder resulting from degenerative arthritis, rheumatoid arthritis or post-traumatic arthritis
- Failed previous total shoulder replacement, resurfacing or other procedure

9.2. EXCLUSION CRITERIA

- a. Subject has an active or suspected latent infection in or about the shoulder joint.
- b. Subject has mental or neuromuscular disorder which would create an unacceptable risk of prosthesis instability, prosthesis fixation failure or complications in postoperative care.
- c. Subject has bone stock compromised by disease, infection or prior implantation which cannot provide adequate support and/or fixation to the prosthesis.
- d. Subject has anticipated activities which would impose high stresses on the prosthesis and its fixation.
- e. Subject is obese such that he/she produces a load on the prosthesis which can lead to failure of fixation of the device or to failure of the device itself.
- f. Subject has absent, irreparable or non-functioning rotator cuff and other essential muscles.
- g. Subject has concomitant disease(s) which may significantly affect the clinical outcome.
- h. Subject has traumatic or pathologic fracture of the proximal humerus.

9.3. WITHDRAWAL CRITERIA

If during the clinical investigation a subject must be withdrawn prematurely, then the procedures outlined in this section must be followed. These procedures should not interfere with the initiation of any new treatments that are necessary to treat a subject's condition. Information on all withdrawn subjects will be documented.

Subjects may be withdrawn from the clinical investigation for any of the following reasons:

- i. Subject Withdrawal: A subject may voluntarily withdraw from the clinical investigation at any time and for any reason. The subject should be asked when possible, and without any form of coercion, the reason for his/her decision. If the participant withdraws from the clinical investigation completely, then data collected up until the point of withdrawal will be included in the final analysis.
- ii. Lost to Follow-Up (LTFU): A subject will be considered LTFU after all reasonable efforts have been made to contact the subject and request his/her continued participation in the clinical investigation. All attempts to contact the subject must be documented and should include at least two attempts to contact the subject by phone and one attempt via a certified letter. Data collected up until the point where the subject is LTFU will be included in the final analysis.
- iii. Removal of Device or AE/Incident: The discontinuation of a subject's participation in the clinical investigation due to the removal of the ReUnion TSA System or AE/incident that prohibits his/her continued participation must be fully explained. All available information concerning the removal of the device or AE/incident should be provided. Data collected up until the point of removal or AE/incident will be included in the final analysis.
- iv. Death: The discontinuation of a subject's participation in the clinical investigation due to death must be fully explained. All available information concerning the death or AE should be provided. Removal of a subject from continued follow-up in the clinical investigation due to death will not be considered a device failure unless the death is

directly caused by, or attributable to, the ReUnion TSA System. Data collected up until the point of death will be included in the final analysis.

v. Other: A subject may be withdrawn by the investigator if he/she believes it is in the best interest of the subject, or if it is determined by the IRB that a subject's continued participation in the clinical investigation represents an unacceptable risk to the subject. The Sponsor must be notified immediately if this occurs. All data collected up until the point of withdrawal or IRB determination will be included in the final analysis. A subject may also be withdrawn if the subject is non-compliant with the clinical investigation procedures or visits, or if a selection criteria violation is noted after the subject received the clinical investigation treatment and it is determined that the subject should be discontinued. All data collected up until the point of withdrawal will be included in the final analysis.

10. Clinical Investigation Evaluations, Procedures and Assessments

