10.3. FOLLOW-UP EVALUATIONS

Subjects in this clinical investigation will be evaluated at Pre-Operative, Operative/Discharge, and at 6 Weeks (4 weeks – 8 weeks), 6 Months (24 weeks – 28 weeks), 12 Months (48 weeks- 56 weeks), 24 Months (100 weeks – 108 weeks) and annually after the index procedure. The follow-up evaluations will include assessment of device-related AEs/incidents, radiographs and ASES Shoulder Score.

Investigative site personnel will contact subjects prior to their scheduled follow-up evaluations to encourage compliance with clinical investigation visits and participation.

If a subject misses a visit and is outside of the visit window, then every effort should be made to collect data instead of noting the visit as missed.

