10.4. SCHEDULE OF EVENTS

Assessment	Pre-Operative	Operative/ Discharge	6 Weeks ^{a,b} (+/- 2 weeks)	6 Months ^{a,b} (+/- 3 weeks)	12 Months ^{a,b} (+/- 4 weeks)	24 Months ^{a,b} (+/- 4 weeks)	Annually ^b
Informed Consent	X						
Demographics & Medical History	X						

Inclusion/Exclusion	X						
Physical Exam	X		X ^c				
Surgical Procedure		X					
ASES Shoulder Score	X		X ^d				
Image Evaluation ^{e, f}	X	X	X	X	X	X	X
Subject Disposition ^g			X	X	X	X	X
	Device-Related AEs/Incidents & Reoperations will be collected throughout the course of the clinical investigation.						
	
 a. Follow-up visit schedule to reflect Institutions' Standard of Care practices b. If the subject misses a visit and is outside of the visit window, then every effort should be made to collect data instead of noting visit as missed. c. Evaluation may be collected when subject presents in-clinic for study visit. d. Evaluation can be collected via phone. e. Radiograph collection should follow Institution's Standard of Care practices and no additional x-rays should be made for study purposes. f. CT scans may be collected if part of Institution's Standard of Care practices. g. Subject Disposition assessment will occur at any time point for subject withdrawal prior to the completion of the clinical investigation. 						

Table 1: Schedule of Events

11. Statistical Methods

The 24 months post-operative results for subjects implanted with the ReUnion TSA System will be compared to a historical group and results reported by respective clinical outcome data in the scientific literature. The benchmark sources and values will serve as the control group for the ReUnion TSA System subjects.

Hypotheses are developed to allow for a comparison of 24 months post-operative ASES Shoulder Score results and 24 months effectiveness/performance between these two populations.

The Statistical Analysis Plan (SAP) lists all variables/questions within this clinical investigation. Therefore, no additional “evaluation” chapter is required nor needed for this CIP.

Data will be captured via IBM Clinical Development electronic data capture (EDC) system and statistical analysis will be performed using IBM SPSS. All statistical hypotheses tests will be with confidence levels (1- α) of 95% and power (1- β) of 80%. The significance level (α) is 0.05 and the beta-value (β) is set to 0.20. Therefore, p-values ≤ 0.05 will indicate statistical significance.

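### Section 9.3(v) allows follow-up of a subject who already carries the implant to be ended for non-compliance or a late-found selection violation, giving up outcome and safety data that could still be collected

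*Protocol*

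**What the plan says.** Protocol 9.3, item v, first covers withdrawal in the subject's best interest or on an IRB finding of unacceptable risk. It then adds two administrative grounds. The first is: "A subject may also be withdrawn if the subject is non-compliant with the clinical investigation procedures or visits". The second applies "if a selection criteria violation is noted after the subject received the clinical investigation treatment and it is determined that the subject should be discontinued". The consequence for analysis is: "All data collected up until the point of withdrawal will be included in the final analysis". SAP 5.3 refers back to the Protocol. Neither document describes collecting ASES scores, device-related events or reoperations after such a withdrawal.

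Other rules bear on the same subjects:

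- **Missed visits** (Protocol 10.3, and footnote b of the schedule in 10.4): when a visit is missed and its window has passed, "every effort should be made to collect data instead of noting the visit as missed".
- **Mode of collection** (footnote d): "Evaluation can be collected via phone". SAP Table 4.4 attaches this footnote to the ASES at every follow-up visit.
- **Primary measure** (Protocol 11.3.2, SAP 3.1.1): the ASES is repeated each year in every subject in whom all or part of the prosthesis remains.
- **Safety and survivorship** (Protocol 8.2): assessed up to 10 years.
- **Populations** (Protocol 11.2, SAP 5.1): ITT is all enrolled subjects. PP drops, at analysis, those who fail eligibility or have a deviation likely to affect outcome.
- **Lost to follow-up** (Protocol 9.3, item ii): assigned after all reasonable efforts. The documented attempts "should include at least two attempts to contact the subject by phone and one attempt via a certified letter".

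**The concern.** The treatment is a single implantation. Withdrawing a subject afterwards does not undo exposure; it only stops the study from seeing what happens next. A rule that lets the site or sponsor stop looking because a subject attends poorly, or because an eligibility error comes to light, gives up data that the plan elsewhere asks for and has a cheap way to obtain.

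Two results are exposed. One is the 24-month ASES mean, if withdrawal comes before that visit. The other is the set of long-term Kaplan-Meier curves for device-related events and reoperation, where an event-free subject is censored at the last available visit and anything later goes unseen. Nothing downstream repairs the loss: Protocol 11.4 and SAP 4.6 only count missing cases, with no imputation or sensitivity analysis. The study is also unblinded, and no threshold is set for non-compliance.

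**Working it through.** **1. The rules side by side.**

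| Subject with implant in place | Under 9.3(v) | Under the other sections |
|---|---|---|
| Misses visits or procedures | May be withdrawn; data stop | 10.3 and footnote b: try to obtain the data. 11.3.2: annual ASES. 8.2: safety to 10 years |
| Selection violation found after surgery | May be withdrawn if so determined; data stop | 11.2: excluded from PP at analysis, which needs no end to follow-up |

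A site can follow both columns by never using the discretion, so this is a tension rather than a strict contradiction. Once the discretion is used, 11.3.2 and 8.2 are no longer met for that subject.

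**2. Which analysis is affected.** A non-compliant subject stays in PP unless the deviation is judged likely to affect outcome, so a lost 24-month score can alter the mean in both PP and ITT. A late-found ineligible subject leaves the PP mean whether or not follow-up continues. For that subject the loss touches only ITT (reported only in the final report) and the long-term curves. This reads ITT as including subjects later found ineligible, as the PP exclusion list implies.

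**3. The plan's own figure.** Inputs from Protocol 11: mean 82.16, test value 65.40, SD 16.76, n = 10, two-sided alpha 0.05. Noncentrality = (82.16 − 65.40)/16.76 × √10 = 3.162, with 9 degrees of freedom. The one-sample t-test power is 0.8031, which agrees with the stated 80.3%. With many more than 10 scores expected, power is not the issue; bias is.

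**4. Bias in the 24-month mean.** Let w be the share of subjects withdrawn this way before 24 months, C the mean of those remaining, and C − g the mean the withdrawn would have had. The full-cohort mean is (1 − w)C + w(C − g) = C − wg, so the observed mean is too high by w × g. The documents give neither w nor g, nor the sign of g. All values below are assumed.

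| w | g (points) | Bias w × g | Bias / 16.76 |
|---|---|---|---|
| 5% | 10 | 0.5 | 3% |
| 10% | 20 | 2.0 | 12% |
| 20% | 20 | 4.0 | 24% |

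**5. Effect on the decision.** With 90 scores and SD 16.76, the one-sided 5% t-test against 65.40 passes when the observed mean exceeds 68.34; with 70 scores, 68.74. If the full-cohort mean is 82.16, a 4-point bias puts the observed mean at 86.16 or, with the opposite sign, 78.16. Both pass easily.

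The bias matters only near the boundary. If the full-cohort mean were exactly 65.40, 100 subjects were enrolled and these were the only losses, the chance of passing would be about 9% (n = 95, bias 0.5), 30% (n = 90, bias 2) and 68% (n = 80, bias 4), against a nominal 5%.

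**6. Long-term curves.** A subject withdrawn at year 1 contributes 1 of 10 planned years; the other 9 are unobserved.

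**The case against.** The case for leaving the text alone has substance.

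- The wording is permissive, and the selection route needs a further decision to discontinue. A reader might infer that these data are never collected. That is true only of subjects actually withdrawn and, for the primary score, only if withdrawn before 24 months.
- Sites are already steered towards retention: 10.3 has them contact subjects before visits and pursue missed data. That stands, but it does not extend to a subject who has been withdrawn.
- A reader might infer that selection errors come to light mainly after poor results, which would fix the direction of bias. The documents do not support this. The criteria describe patient characteristics recorded before surgery, and SAP 6.2 has them checked during monitoring. Nor do the documents show that poor attenders score lower; subjects who do well may also stop coming.
- A reader might take two calls and a letter as sufficient for loss to follow-up. The standard is all reasonable efforts, and those attempts are the minimum. Nothing bars contact at 24 months, but nothing requires it of a subject already classed as lost.
- A reader might apply the 56% drop-out to the 24-month visit and argue from lost precision. That figure is an overall rate taken from a study with at least 10 years of follow-up, so it does not give the 24-month loss.

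The objection limits the size and certainty of the harm. It does not supply a reason to stop observing a subject who still has the device and has not withdrawn consent.

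**Conclusion.** The point holds as an avoidable weakness in the follow-up rules. Section 9.3(v) permits the end of data collection in implanted subjects on two grounds that the plan can handle without it, and no section restores follow-up afterwards. For non-compliant subjects it can affect the 24-month mean in PP and ITT; for late-found ineligible subjects, only ITT and the long-term curves.

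Size and direction are unknown. The 0.5 to 4 points shown rest on assumed shares of 5% to 20% and assumed gaps of 10 to 20 points, with the withdrawn scoring lower. Bias of that order would not alter the non-inferiority conclusion if the true mean is near 82, so this is no threat to the primary result under the plan's own assumptions. It bears on the accuracy of the reported mean and the completeness of long-term safety data. Follow-up not collected at the time is unlikely to be fully recoverable, so the change is worth making now.

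**What to change.** In Protocol 9.3(v), state that non-compliance, or a selection violation found after treatment, does not by itself end follow-up of an implanted subject. ASES by phone, device-related events, reoperations and vital status continue to be collected unless consent is withdrawn or was not valid, and the violation is dealt with through the PP definition in 11.2. The exception for invalid consent is needed because consent is itself a selection criterion. Leave the best-interest, IRB and voluntary-withdrawal grounds as they are.

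In 9.3(ii), add that a subject who could not be reached at an earlier visit is contacted again at the 24-month window. Align SAP 5.3, which relies on the Protocol text.

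The cost is protocol wording and some extra calls to non-attending subjects, with no new procedure. The sponsor should accept that the mean may turn out less favourable.

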10.1. METHOD OF ASSIGNING SUBJECTS

No specific methods (e.g. randomization, blinding, or stratification) for assigning subjects are used in this clinical investigation plan (CIP). Consecutive subjects at each site meeting all eligibility criteria will be enrolled in this clinical investigation.

